#### **2.4.2.8.2 Analysis of Quality of Life (QOL) Assessment**

QOL assessments for the overall Respiratory Complaints scale score will be analyzed descriptively at each time-point (Baseline, 1-month, 3-month, 6-month) using n, mean, standard deviation, minimum, median, and maximum. Change from baseline values will also be presented in a similar manner. Individual responses to each Respiratory Complaints survey question will be summarized descriptively using frequencies and percentages. The Severe Respiratory Insufficiency Questionnaire guidance for scoring the Respiratory Complaints scale will be implemented.

### Guidance for scoring

Please provide the following values for each item:

completely untrue	=>	1
mostly untrue	=>	2
sometimes true	=>	3
mostly true	=>	4
always true	=>	5

The majority of items need to be recoded following the instructions given below:

value	recoded value	Items which need to be recoded:
1	→ 5	
2	→ 4	
3	→ 3	
4	→ 2	
5	→ 1	1, 2, 4, 5, 6, 8, 11, 12, 13, 14, 15, 16, 17, 19, 21, 22, 23, 24, 25, 26, 28, 29, 30, 31, 34, 35, 38, 39, 40, 42, 43, 45, 46, 47, 48.

Next, the scales need to be calculated as indicated below. For this purpose at least 50% of the items per scale must be correctly addressed. Please find the item number indicated in brackets [a, b, c.....]. This process of transformation produces a score between 0 and 100 with higher values indicating a better health-related quality of life according to content of the scale.

### Respiratory Complaints

$$SRI - RC = \frac{\text{Mean } [2,5,12,19,22,24,25,29] - 1}{4} \cdot 100$$

#### 2.4.2.9 Patient/caregiver Satisfaction with Therapy

##### 2.4.2.9.1 Derivation of Patient/caregiver Satisfaction with Therapy

Satisfaction questionnaire results for prior therapy at baseline and for The Volara® System at 1-month, 3-month and 6-month study visits will be recorded in the data.

##### 2.4.2.9.2 Analysis of Patient/caregiver Satisfaction with Therapy

Patient/caregiver satisfaction with prior therapy at baseline and with The Volara® System at 1-month, 3-month, and 6-month timepoints will be analyzed descriptively using frequencies and percentages. Patient/caregiver satisfaction scores will be summarized for each question.

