3.3.3.1 Baseline Study Visit: During the baseline visit, study staff will review the informed consent form (and assent form if minor subject) with the study subject and/or caregiver(s). If the patient/caregiver agrees to participate in the study, the informed consent form (and assent form, if applicable) will be signed. A pregnancy test will be administered to female subjects of childbearing age. Inclusion and exclusion criteria will then be assessed and documented and (if eligible) the subject will be enrolled in the study. The study schedule and subject responsibilities will then be reviewed with the subject/caregiver. During the Baseline Visit, the subject's current respiratory therapy regimen and required respiratory support will be documented. A quality of life (QOL) assessment using the Severe Respiratory Insufficiency (SRI) questionnaire will be completed for each subject to assess QOL rating during the pre-treatment period and a Satisfaction Survey questionnaire will be completed by the subject and/or caregiver as an assessment of the current therapy regimen.

3.3.3.2 Documentation of Demographics, Medical History and Pulmonary Exacerbations: Demographic data will be collected for patients enrolled in the study. Medical records for each enrolled subject will be obtained and reviewed to obtain relevant patient medical history and to document pulmonary comorbidities and history at the time of enrollment. Current respiratory related medications and treatments will be documented. Pulmonary exacerbations (as defined in the study endpoints) that occurred in the 12-month period prior to enrollment in the study will be documented. Subsequent medical records will be obtained during the active treatment period and will be used to determine and to document the occurrence of pulmonary exacerbations during that period.

- **Demographic Data**

The following demographic data will be collected: Age, Height, Weight, Race, Ethnicity and Gender.

PROTOCOL TITLE

Evaluation of Oscillation and Lung Expansion (OLE) using The Volara® System for treatment of respiratory complications in patients with neuromuscular disease in the home setting

Final Protocol

Protocol Number: CR-RR-2020-005

Date: 11May2022

- **Pulmonary Related Medical History**

History of asthma, cystic fibrosis, bronchiectasis, COPD, obstructive sleep apnea, documented obesity (BMI $\geq 30 \text{ kg m}^2$), other pulmonary condition(s) will be documented.

- **Medications**

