A satisfaction questionnaire will be administered to all study subjects/caregivers by the study staff at baseline (reflecting the patient's pre-treatment therapy regimen) and at each subsequent study visit to assess satisfaction with OLE therapy. Results will be determined for each subject and for the study group for each time period and will then be compared to determine any differences in satisfaction scores between the pre-treatment and active treatment time periods.

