3.5.2 Statistical Analysis

- Summary statistics and data listings will be provided.
- Demographic data will be summarized. For continuous type data (e. g. Age), descriptive summary statistics (N, mean, median, standard deviation, min, and max) will be presented. For categorical variables (gender, race, etc.) the number and percent of subjects in each category will be provided.
- Endpoints will be documented and compared as described below:

Primary Endpoints:

Frequency of Exacerbation of Pulmonary Disease (as defined in section 3.3.4.1) along with 95% confidence interval will be generated. A detailed description of the analysis plan along with specific subsets to be summarized will be described in a separate document (the statistical analysis plan).

Secondary Endpoints:

The secondary endpoints (listed in section 3.3.4.2) will be summarized with descriptive summary statistics appropriate for continuous or categorical data, depending on the outcome being summarized:

1. Hospital Admissions
2. Hospital LOS
3. ICU Admissions

PROTOCOL TITLE**Evaluation of Oscillation and Lung Expansion (OLE) using The Volara® System for treatment of respiratory complications in patients with neuromuscular disease in the home setting****Final Protocol****Protocol Number:** CR-RR-2020-005**Date:** 11May2022

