4. ICU LOS
5. Number of Outpatient Visits
6. Antibiotic Use Days
7. Pulmonary Function Testing
 - SVC
 - PCF
 - Resting SpO₂
 - MIP
8. QOL Assessment
9. Adherence to OLE Therapy Regimen
10. Patient/Caregiver Satisfaction

Comparison of Pre-treatment and Active Treatment Periods

Rate of exacerbation and health care utilization will be evaluated to compare the active treatment period and the control periods (six-month period immediately prior to active treatment and six-month seasonally equivalent time-period). Remaining endpoints will compare baseline assessments to assessments obtained during the active treatment period. Comparisons will be conducted for the purpose of identifying any statistical associations that can be attributed to use of OLE treatment with The Volara® System.

General Study Information**4.1 Technical Support for Device(s)**

Technical support will be performed by Hillrom following routine service practices (contact details will be provided).

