## 3. CHANGES FROM ANALYSIS PLANNED IN PROTOCOL

Mean adherence to prescribed treatment regimen will not be analyzed.

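### The protocol's pre-treatment versus active-treatment comparison of satisfaction has no within-patient summary in the SAP, the omission is not declared, and the two separate tables can show a gain that comes only from who is still answering

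*SAP*

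**What the plan says.** **Protocol.** Section 3.1.1 makes subjects their own controls and says that the baseline satisfaction survey is to be compared with results from the active treatment period. Section 3.3.4.2 says that satisfaction results are determined for each subject and for the group, and "will then be compared to determine any differences in satisfaction scores between the pre-treatment and active treatment time periods". Section 3.5.2, under the comparison of periods, adds: "Remaining endpoints will compare baseline assessments to assessments obtained during the active treatment period". The same section says that the secondary endpoints "will be summarized with descriptive summary statistics appropriate for continuous or categorical data"; it names no paired method.

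**SAP.** Section 1.2.1 restates the sentence from protocol 3.1.1 but leaves out the comparison. Section 2.4.2.9.2 plans counts and percentages only ("Patient/caregiver satisfaction with prior therapy at baseline and with The Volara® System at 1-month, 3-month, and 6-month timepoints will be analyzed descriptively using frequencies and" …), summarised question by question. Appendix 1 puts prior therapy in Table 14.2.5.1 and Volara in Table 14.2.5.2, both on the FAS. Listing 16.2.6.5 shows both sets of ratings. Sections 2.4.2.1.2 and 2.4.2.8.2 plan change from baseline for pulmonary function and quality of life; satisfaction has no counterpart. Section 2.6.1 uses data up to dropout without imputation. Section 3, on departures from the protocol, has one entry: "Mean adherence to prescribed treatment regimen will not be analyzed".

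**The concern.** A comparison named in the protocol is not carried into the SAP as a summary, and the SAP does not say so. Readers will still make the comparison by setting Table 14.2.5.2 against Table 14.2.5.1. Neither table is limited to patients who answered at both times, so the difference mixes change within patients with change in who is answering.

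The likely direction of that mixing matters. The protocol's withdrawal reasons (Synopsis, and the study exit section) include not tolerating OLE and being unable or unwilling to perform it. Such patients may well be the less satisfied ones, and they drop out of the later percentages. That would favour the device in an open-label rating of Volara against the therapy it replaces.

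**Working it through.** **Is there a figure to reproduce?** No. The documents give no effect size, dropout rate or satisfaction rate for this endpoint, and the sample of about 70 is a convenience sample. The check is therefore a direct count under stated assumptions.

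**Inputs.**
- N = 70 (protocol and SAP sample size). Assumed: all 70 are in the FAS and answer at baseline.
- Assumed: one question, scored satisfied or not satisfied. The questionnaire is not in the documents.
- Assumed: 40–70% satisfied at baseline, and 10–30% lost by 6 months.
- Assumed share of leavers who are dissatisfied: the same as in the whole group, 80%, or 100%.
- By construction, no patient's rating changes.

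**Formula.** Let S be the number satisfied at baseline, L the number lost and Ls the satisfied patients among those lost, each rounded to whole patients.

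Apparent gain = (S − Ls)/(N − L) − S/N

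**Worked case: 60% satisfied, 20% lost.** S = 42 and L = 14.
- All leavers dissatisfied (Ls = 0): 42/56 = 75.0% against 42/70 = 60.0%, a gain of 15.0 points.
- 80% of leavers dissatisfied (0.8 × 14 = 11.2, so 11; Ls = 3): 39/56 = 69.6%, a gain of 9.6 points.
- Leavers as the whole group (6 dissatisfied; Ls = 8): 34/56 = 60.7%, a gain of 0.7 points, from rounding only.

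**Full grid: apparent gain in points, with a true within-patient change of zero.**

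| Satisfied at baseline | Loss | Leavers as whole group | 80% of leavers dissatisfied | All leavers dissatisfied |
|---|---|---|---|---|
| 40% (28/70) | 10% | −0.3 | +2.9 | +4.4 |
| | 20% | −0.7 | +4.6 | +10.0 |
| | 30% | +0.8 | +9.0 | +17.1 |
| 50% (35/70) | 10% | +0.8 | +4.0 | +5.6 |
| | 20% | 0.0 | +7.1 | +12.5 |
| | 30% | −1.0 | +13.3 | +21.4 |
| 60% (42/70) | 10% | +0.3 | +5.1 | +6.7 |
| | 20% | +0.7 | +9.6 | +15.0 |
| | 30% | −0.8 | +17.6 | +25.7 |
| 70% (49/70) | 10% | −0.2 | +6.2 | +7.8 |
| | 20% | −0.4 | +12.1 | +17.5 |
| | 30% | −0.6 | +21.8 | +30.0 |

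With no loss, the gain is exactly 0 in every row.

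**The same cases restricted to patients with both ratings.** In the worked case with all leavers dissatisfied, baseline is 42/56 = 75.0% and 6 months is 42/56 = 75.0%, a gain of 0. This holds in every zero-change case, because both percentages come from the same people.

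**What separate percentages hide even with no loss.** Suppose 56 patients answer both times, 28 satisfied at baseline and 35 later. Improved minus worsened must be 35 − 28 = 7. Those worsening can number at most min(28, 56 − 35) = 21. The tables therefore fit anything from 7 improved and 0 worsened to 28 improved and 21 worsened.

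**The case against.** The strongest reply is that the study is descriptive with no formal testing (SAP 1.2.2 and 2.6.3), that the protocol never asks for a paired analysis, and that percentages at baseline and at each visit already permit a group comparison. Listing 16.2.6.5 also keeps the individual ratings matchable. Much of this stands: no data are lost, and a group-level comparison by eye is possible. It does not answer the point. A shift table is itself descriptive, the protocol speaks of results per subject and of subjects as their own controls, and a listing is not a summary. A general statement that nothing is tested does not declare that a planned descriptive comparison has gone.

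A reader might infer more than the documents support:

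- *That the two tables use different patient sets.* Both are assigned to the FAS. Respondents differ only through dropout, missed forms or having no prior regimen to rate.
- *That many patients have no prior therapy, which by itself creates a gain.* Eligibility (protocol 3.2.1) does not require one, and the SAP does not say how such patients are handled. But the protocol presumes a regular regimen: the Synopsis describes the baseline period that way, and the baseline form is "completed by the subject and/or caregiver as an assessment of the current therapy regimen". Any such patient would add to the mismatch, but no number is given and no size can be attached.
- *That this is the trial's only direct preference comparison.* The questionnaire is not in the documents, so its items cannot be judged.
- *That a change of rater biases the result.* Subject and/or caregiver may answer, and no rule keeps the respondent constant. Nothing shows whether rater type is recorded or how often it would change.

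**Conclusion.** The point holds in limited form. The SAP has no within-patient summary of satisfaction, although the protocol plans a comparison between periods and the SAP keeps change from baseline for pulmonary function and quality of life. Section 3 does not declare the omission.

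Under the assumptions above, loss related to satisfaction produces a false gain of about 3 to 22 points when 80% of leavers are dissatisfied and about 4 to 30 points when all are. A reader might take this as a prediction that the tables will overstate satisfaction. It is not: the documents give no dropout or satisfaction rates, and the artefact is about zero if loss is absent or unrelated to satisfaction.

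This concerns one secondary endpoint of an open-label pilot. It does not touch the primary endpoint or safety, but it should be corrected because the remedy is cheap.

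**What to change.** In SAP 2.4.2.9.2, for each question asked at both times, add a baseline-by-visit shift table at 1, 3 and 6 months. Limit it to FAS subjects who rated both prior therapy and Volara, and give n at each visit. Summarise subjects without a prior-therapy rating separately. Note rater type, or restrict by it, only if it is recorded.

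If the sponsor keeps frequencies only, enter the dropped comparison in SAP section 3 and state with Tables 14.2.5.1 and 14.2.5.2 that they rest on available respondents, who may differ by visit.

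The cost is a paragraph of SAP text and one more table from ratings already planned for collection. The paired table will have a smaller n. It removes the effect of changing respondents but still describes only those who answered both times, so n per visit must be read with it.

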### 2.5 Safety Analyses

All safety analyses will be performed on the SS.

#### 2.5.1 Adverse Events

##### 2.5.1.1 Derivation of Adverse Events

*Pre-treatment adverse event* – An adverse event that starts between the date of signing the informed consent form (ICF) and the start of study therapy

*Treatment-emergent adverse event (TEAE)* – An adverse event that starts on or after the start of study therapy

In case of incomplete information on study treatment or AE onset, events will be classified as treatment-emergent unless there is sufficient data to rule out the possibility that the event started after the start of study treatment.

The number of events per patient will be calculated as follows:

$$\frac{\text{Number of Total Events}}{\text{Number of Patients in Safety Set}}$$

##### 2.5.1.2 Analysis of Adverse Events

An AE overview summary table will be prepared to include the number of patients, the percentage of patients (%), the number of events, and the number of events per patient, for the following categories:

1. Any adverse event
2. Any treatment-emergent adverse event (TEAEs)
3. Treatment emergent non-serious AEs
4. Treatment-emergent serious AEs (SAEs)
5. Treatment-emergent study device-related AEs
6. Treatment-emergent study device-related SAEs
7. Treatment-emergent AEs leading to discontinuation
8. Treatment-emergent AEs leading to death

Additional listings and tables on the above categories (with the exception of #1 and #3) will be given by SOC and PT. Pre-treatment AEs (those occurring between informed consent and device use) will also be listed. For SAE listings, the seriousness criteria will be included in the listing.

The tables below will display the total number of patients, the percentage of patients (%), the number of events, the number of events per patient, system organ class (SOC), and preferred term. Table summaries will be produced for:

- Treatment-emergent AEs by severity
- Treatment-emergent SAEs by severity
- Treatment-emergent AEs by relationship to study device
- Treatment-emergent SAEs by relationship to study device
- Treatment-emergent adverse events in  $\geq 5\%$  of patients

Tables by preferred term and tables by system organ class (SOC) and preferred term will be sorted in descending order by the percentage of patients.

Adverse event listings will be sorted by patient ID, and adverse event start date. They will include SOC, PT, verbatim term, adverse event start and end date and its duration, relationship to study device, severity, action taken, and seriousness.

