| | 
• Airway Clearance Satisfaction surveys will be conducted. Results from the active treatment period will be compared to the baseline period, during which the subject received his/her regular airway clearance regimen.Any device related adverse events which occur after initial therapy with The Volara® System will be recorded.Any equipment related complaints which occur after initial therapy with The Volara® System will be recorded. |
| Subject Withdrawal: | Subjects may withdraw consent to participate in the study at any time. The subject may also be withdrawn from the study according to investigator judgement regarding the continued health or safety of the subject or related to inability or unwillingness to perform study therapy or procedures. Removal of subjects may occur for any of the following reasons: 
• Subject enrolled in violation of inclusion/exclusion criteria• Inability to tolerate OLE therapy• Adverse event or adverse device effect that occurs during therapy• Physician judgement that the patient is not a good candidate for the study• Inability or unwillingness to perform OLE therapy and data collection maneuvers as directed |
| Statistical Methods: | Descriptive summary statistics will be provided for demographics, the primary and secondary endpoints. Continuous data will be summarized with N, mean, median, standard deviation, min, and max. Categorical data will be summarized with the number and percent of patients in each category. Incidence of adverse device effects (ADEs) will be tabulated. |

PROTOCOL TITLE

Evaluation of Oscillation and Lung Expansion (OLE) using The Volara® System for treatment of respiratory complications in patients with neuromuscular disease in the home setting

Final Protocol

Protocol Number: CR-RR-2020-005

Date: 11May2022

| | |
|--|---|
| | Incidence of device-related complaints will be tabulated. |
|--|---|

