3.3.3.5 Home Training on The Volara® System: A Hillrom designated trainer will set up the device and review operation and treatment protocol at the time the device is delivered. Study subjects and caregivers will be instructed to use the device as their primary airway clearance and lung expansion therapy for a period of six months. Hillrom training staff will follow up with each Volara user according to the standard device placement and follow-up program.

3.3.3.6 Adherence Documentation: During the six-month follow-up period, adherence to the daily prescribed therapy regimen will be assessed. The Volara® System logs therapy details for each therapy completed, including the total time of therapy, the number of stages completed, the total time in CPEP mode, total time in CHFO mode and peak pressures achieved in each mode. Adherence data logs will be downloaded on a regular basis during the active treatment period.

3.3.3.8 One-month Virtual Study Visit: A one-month study visit with each study subject will be conducted virtually. Visits will be completed +/- 3 days from the one-month scheduled visit date. During this visit, the following procedures and assessments will be conducted:

- Review of study procedures with subject/caregiver
- Review of current respiratory status, respiratory treatments, and medications
- Documentation of patient/caregiver reported exacerbations and medical interventions for the prior period (run-in and first month of Volara therapy)
- Documentation of any Adverse Device Effects that the subject experienced during the follow-up period
- Completion of QOL questionnaire
- Completion of Patient/Caregiver Satisfaction survey

3.3.3.9 Three-month and Six-month Virtual Study Visits: Three-month and six-month study visits with each study subject will be conducted virtually by study staff. Visits will be completed

PROTOCOL TITLE

Evaluation of Oscillation and Lung Expansion (OLE) using The Volara® System for treatment of respiratory complications in patients with neuromuscular disease in the home setting

Final Protocol

Protocol Number: CR-RR-2020-005**Date:** 11May2022

+/- 3 days from the one-month scheduled visit date. During these visits, the following procedures and assessments will be conducted:

- Review of study procedures with subject/caregiver
- Review of current respiratory status, respiratory treatments, and medications

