3.3.5 Study Observations/Procedures Table

The study observations and documentation timeline are outlined in Table 1.

PROTOCOL TITLE

Evaluation of Oscillation and Lung Expansion (OLE) using The Volara® System for treatment of respiratory complications in patients with neuromuscular disease in the home setting

Final Protocol

Protocol Number: CR-RR-2020-005

Date: 11May2022

TABLE 1

Study Observations/Procedures

| Procedures | Baseline | Run-in | 1 month | 3 months | 6 months |
|---|------------------------------------|--------|---------|----------|------------------------------|
| Inclusion/Exclusion Criteria | X | | | | |
| Pregnancy test (women of childbearing age) | X | | | | |
| Informed consent (and assent if minor subject) | X ¹ | | | | |
| Demographics | X | | | | |
| Medical History | X | | | | |
| Baseline Pulmonary Medications | X | | | | |
| Documentation of acute pulmonary exacerbations: 
 Hospital admission and discharge (including ICU admission and discharge) Antibiotic use (IV/Oral/inhaled) start and stop dates Outpatient Visits for Pulmonary Complication 
 Physician Office Visits Urgent Care Visits ED Visits Documented from the medical record | X Retrospective (past 12 mo) | | | | X Active Treatment Period |
| QOL Questionnaire | X | | X | X | X |
| Patient/Caregiver satisfaction with Therapy | X | | X | X | X |
| Basic Pulmonary Function Measures 
 SVC PCF Resting SpO₂ Maximal Inspiratory Pressure (MIP) | X | | | | Monthly |
| Adherence to prescribed regimen (OLE) | | | | | Ongoing |
| Documentation of use of MIE or other airway clearance/lung expansion therapy/maneuvers | | X | | | |
| Adverse device effects | | | | | Each Occurrence |
| Study Exit Form | | | | | X |

PROTOCOL TITLE

Evaluation of Oscillation and Lung Expansion (OLE) using The Volara® System for treatment of respiratory complications in patients with neuromuscular disease in the home setting

Final Protocol

Protocol Number: CR-RR-2020-005

[figure not shown]
Date: 11 May 2022

¹Obtained prior to any study-specific procedures

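### The SAP plans all-cause adverse event outputs where the protocol requires only device effects, complaints and deaths to be recorded or reported, drops the promised complaint table, and lists neither difference in section 3

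*SAP*

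**What the plan says.** **Protocol, what is to be recorded.** The synopsis (Methods) provides for recording "Any device related adverse events which occur after initial therapy with" the device, and for recording equipment complaints over the same time. The one-month visit (3.3.3.8) calls for "Documentation of any Adverse Device Effects that the subject experienced during the follow-up period". The three- and six-month visit lists (3.3.3.9) name no safety item. The only adverse-event row in Table 1 is "Adverse device effects". Section 5.0 names two reportable events, ADEs and device complaints. Section 5.6 adds all deaths. Section 6.1 requires immediate reporting of serious and unanticipated device effects.

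**Protocol, what is to be analysed.** The synopsis (Statistical Methods) makes two commitments: "Incidence of adverse device effects (ADEs) will be tabulated" and "Incidence of device-related complaints will be tabulated". Section 3.5.2 adds no safety analysis.

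**Protocol, wider wording.** Sections 5.2 and 5.3 define AEs and SAEs whatever their relation to the device. The synopsis (Subject Withdrawal) allows removal for "Adverse event or adverse device effect that occurs during therapy".

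**SAP.** Section 2.5.1.1 defines pre-treatment AEs from the date of consent. Section 2.5.1.2 plans an overview whose rows include "Any treatment-emergent adverse event (TEAEs"), all serious events, and device-related subsets shown separately. Appendix 1 carries these into tables 14.3.1.1.1 to 14.3.1.3.2 and listings 16.2.7.1.1 to 16.2.7.1.8. Section 3 reports one change from the protocol, the dropping of the adherence analysis.

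**The concern.** The SAP summarises classes of event that the protocol does not tell sites to record, and leaves out a safety tabulation that the protocol promises. Readers normally take a table of treatment-emergent or serious events as all-cause incidence, and an empty pre-treatment listing as meaning that nothing happened. Under the protocol's collection text, the first would mean device-attributed events plus any deaths entered as AEs. The second would mean that such events were not systematically collected. Nothing in the SAP warns the reader of this.

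The gap is most visible for hospital admissions. An unplanned respiratory admission counts towards the primary endpoint and also meets the SAE definition in protocol 5.3. Under the protocol's collection text it would enter the SAE tables only if attributed to the device. One report could then show many admissions and few SAEs, with no explanation.

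**Working it through.** There is no plan figure to reproduce: the sample is a convenience sample and no safety rate is stated. The check compares the two documents and counts the planned outputs.

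**1. Scope, item by item.**

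| Item | Protocol recording, reporting and analysis text | SAP 2.5.1 and Appendix 1 |
|---|---|---|
| ADEs, serious ADEs | Required; ADE incidence tabulated | Covered (14.3.1.1.4, 14.3.1.1.5, relationship splits) |
| Unrelated AEs and SAEs | Defined (5.2, 5.3); no instruction to record or report | Covered by the any-AE, treatment-emergent and SAE outputs |
| AEs before first therapy | No clear instruction; the synopsis starts recording after first therapy | Listings 16.2.7.1.1 and 16.2.7.1.3 |
| Deaths | All reported (5.6) | 14.3.1.1.7 and 16.2.7.1.8 |
| Device complaints | Recorded and tabulated (synopsis) | None |

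**2. Complaint outputs (SAP Appendix 1).**
- Tables: 5 (14.1.x) + 8 (14.2.x) + 12 (14.3.x) = 25.
- Listings: 7 (16.2.1 to 16.2.4.4) + 6 (16.2.6.x) + 8 (16.2.7.x) = 21.
- Total: 25 + 21 = 46, of which 0 cover device complaints. The word occurs there only in the name of the Respiratory Complaints quality-of-life scale.

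**3. Disclosure.** Section 3 contains one item, adherence. Of the two safety differences (AE scope and complaint table) it lists 0.

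**4. If collection followed the protocol text.** Leaving aside any unrelated death entered as an AE:
- Table 14.3.1.1.2 would repeat 14.3.1.1.4, and 14.3.1.1.3 would repeat 14.3.1.1.5.
- Listing 16.2.7.1.2 would repeat 16.2.7.1.5, and 16.2.7.1.4 would repeat 16.2.7.1.6.
- In the eight-row overview 14.3.1.1.1, rows 1, 2 and 5 would agree, as would rows 4 and 6. With rows 3, 7 and 8, that leaves at most 5 distinct results.
- Respiratory events in the run-in would not be lost altogether. The one-month visit documents patient- or caregiver-reported "exacerbations and medical interventions for the prior period (run-in and first month of Volara therapy"), so they are captured as exacerbations but not as AEs.

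**5. If the case report form collected all AEs.** The overlap in step 4 is no longer built in. Steps 2 and 3 stand unchanged.

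**The case against.** The strongest reply is that the case report form may well have collected all AEs. It is not among the documents. The protocol defines all-cause AEs and SAEs, lists any AE as a possible reason for removal, and requires care for any adverse event (6.1). The SAP names AEs as well as ADEs as safety variables (1.3.3.1), mentions problems with SAE reporting (1.3.1), and plans fields for relationship, severity and action taken, which suit a general AE form. Against this, the reasons for leaving the study in SAP 2.1.4 include an adverse device effect but no general AE. Neither side is conclusive. A reader might infer that the protocol's safety text is confined to device effects, or that unrelated events were missed. The documents support neither inference: it is the instructions to record, report and tabulate that are narrower.

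A reader might also be tempted to count the four repeated outputs in step 4 with the two pre-treatment listings, and call 6 of the 20 AE outputs redundant or empty. That depends on the unseen case report form. It also depends on one reading of protocol 5.0, which names both consent and first treatment as the start of surveillance, so some sites may have started at consent. It should not serve as a measure of the problem.

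It is also fair to say that the promised ADE tabulation is kept, that extra tables remove nothing, and that this is a descriptive pilot whose primary endpoint is unaffected. These points limit the seriousness. They do not answer the missing complaint table, which does not depend on how AEs were collected.

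**Conclusion.** The SAP is wrong as written on two counts, and both should be corrected.

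- **Complaints.** The protocol says complaint incidence will be tabulated, from data it says are recorded. None of the 46 outputs does so, and section 3 gives no reason. This holds whatever the case report form contained.
- **Scope of AEs.** The SAP plans all-cause and pre-treatment outputs, while the protocol requires only ADEs, complaints and deaths to be recorded or reported. Section 3 does not mention it. If collection followed the protocol text, outputs titled as all-cause would not be all-cause. If it was wider, only a statement of scope is missing.

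The size in events cannot be derived: nothing in the documents gives the number of unrelated or pre-treatment AEs left uncollected. The finding on disclosure concerns section 3. Some SAP front matter, which may include the revision history, was not available, and no claim is made about it.

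**What to change.** 1. **Complaint table.** Add a device-complaint incidence table on the safety set to SAP 2.5 and Appendix 1, using the complaints that the protocol synopsis says are recorded. Otherwise list the omission and its reason in section 3.
2. **Scope.** State in SAP 2.5 which AEs were collected and from when, and record the difference from the protocol in section 3.
3. **If only ADEs and deaths were collected:**
   - Retitle the treatment-emergent and serious outputs as ADE and serious ADE.
   - Except the death outputs, 14.3.1.1.7 and 16.2.7.1.8. These keep an all-cause title and include every reported death. Treat the death row of 14.3.1.1.1 in the same way.
   - Keep the pre-treatment listings, with a footnote that pre-treatment and unrelated AEs were not systematically collected. Dropping them could hide an event that a site did report.
   - If readers are referred to the hospital and ICU admission listings (SAP 2.4.2.2.2 and 2.4.2.4.2), note that these use the full analysis set, which requires a prior exacerbation, and concern respiratory-related admissions. They do not replace all-cause SAEs in the safety set.
4. **If all AEs were collected:** keep the tables and say in section 3 that collection was wider than the protocol text.

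The cost is SAP wording, titles, footnotes and one table, with no new visits or subject data. Complaint data may need to be drawn from the sponsor's post-market surveillance, which investigates complaints under protocol 5.7, because the documents do not say that they enter the study database. The downside is a narrower safety claim if collection was narrow.
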